#### **c. Data Storage and Confidentiality:**

Information will be obtained from clinical assessments and confidential HIPAA compliant online questionnaires that will be completed on the tablet. Access to activate tablets will be limited to study staff and password protected. Patient and their caregivers will confirm their identity by answering a personal security question at the end of each session. Specific materials obtained in the study will include patient and caregiver reports from behavioral, adherence, treatment satisfaction and QOL assessment tools.

Other information, such as medical history and clinician symptom ratings also will be collected by site staff from clinician notes and/or medical records or directly entered into password protected online databases by the clinicians or patients/caregivers. The following samples will be collected: urine in girls for a pregnancy test, if they confirm menarche. As recommended in standard clinical practice an 8-hour fasting blood draw for serum glucose, insulin, liver function tests, renal panel (including electrolytes),

TSH, HbA1c, and lipid profiles. The results of pregnancy test will be given to parents of minors at the discretion of the clinician. Blood pressure, and anthropometrics including height, weight, BMI, and BMI %ile will be recorded.

As with any study, there is a potential risk of loss of confidentiality. Consistent with the Federal guidelines, all patients and guardians will be informed of the federally mandated reporting laws for child abuse and neglect, verbally and in the written consent form. Therefore, if abuse or neglect is suspected the Department of Human Services will be called. Risks associated with this include embarrassment, legal consequences, and removal of the child from the parents' /legal guardians' home.

**d. Setting:** Assessments will be conducted at the participating community-based private and public mental health treatment centers in the East Coast and Midwest Regions. The participating site personnel will be made up of a real-world clinical trial team that includes members with varied training and experience with appropriate support from a qualified physician and centralized study trial team. Site staff who will be obtaining informed consent, reviewing medication lists, and collecting and assessing adverse events must complete Human Participants Protection and Good Clinical Practice (HPP and GCP) training prior to involvement in the study. These essential study staff will be documented via a site specific delegation of authority (DOA) log. DOA logs will be reviewed by the study monitor at each site visit to ensure that all new essential study staff have been added.

**e. Laboratory methods and facilities:** Participants will be sent for blood work, at the clinician's discretion, to any laboratory facility. No specific laboratory test will be mandated, as it is expected that laboratory procedures will take place in settings where everyday care happens, such as community clinics, hospitals and health systems. It is recommended that clinicians adhere to practice guidelines and labs are ordered through the patient's medical practice by their clinicians.

**f. Estimated Period of Time to Complete the Study:** The following is a timeline for the 72-month period of the proposed study: Months 1-2: Train study personnel; Months 3-57: Recruit an average of approximately 1-2 patients/site/month from 40 sites over 54 months for a total sample size of 1800 patients, we expect 25% of the sample recruited by M10-11; 50% recruited by M30; 75% by M45 and the final patient recruited by M57; Months 34-68: Complete subject participation, data entry, and analyses. Final analyses will be completed M70- after the last patients have completed 6 and 24 months of follow-up.

## **F. HUMAN SUBJECTS**

### **a. Description of Subjects**

We will recruit a total of 1800 youth, (approximately 900 each from ~20 Midwest sites and ~20 East Coast mental health treatment sites) to participate in the proposed patient-centered large pragmatic trial examining the effectiveness of MET and LIFE vs. LIFE alone. Subjects will be eligible to enroll and randomize if they are ages 8-19 years old (inclusive) at the time of screening, overweight or obese (BMI  $\geq 85\%$ ), continuing or starting treatment with at least one SGA (i.e., olanzapine, clozapine, risperidone, quetiapine, aripiprazole, ziprasidone, iloperidone, lurasidone, paliperidone, or asenapine), have a clinical diagnosis of BSD (bipolar I or II disorder, cyclothymia, or bipolar or mood not otherwise specified, or other specified bipolar or mood disorder) and are living at home with their caregivers.

Based on feedback from our advisory board and our consultants including children and adolescents who are in state custody is essential so that our sample is not biased as SGA exposure in this population is extremely high, Therefore, we will allow children and adolescents who are under the custody of DHS to enroll. We will seek the approval of a legally authorized individual from the county (e.g. Hamilton or Butler). This may be the county caseworker or it may be their supervisor. It will NOT be the case manager from the private agency that is handling the placement. But, the private agency case manager

will know who the appointed county JFS social worker. The foster parent(s) will NOT have the authority to authorize enrollment into a research study. We will need the foster parent(s)' approval to ensure that study visits will be attended and compliance with study requirements is manageable. Consents may be faxed for signature to the legally authorized individual as specified from each county. A fully signed copy of the consents will be offered back to JFS after the consenting process occurs.

For youth who reside in Northern KY and are in the custody of the Cabinet for the Commonwealth of Kentucky, we will obtain the permission of the assigned Cabinet Social Worker who is assigned to the individual. That person will determine if they have the authority to grant permission for participation or whether they need to seek higher approval.

For youth in the custody of New York City foster care, the investigator will submit a proposal along with our IRB approval and relevant consent forms to the Administration for Children's Services (ACS). ACS will review, process, and approve the proposal. Once approved the proposal will go to the State Office of Children and Family Services (OCFS) for their review and approval.

**b. Sample Size**

Eighteen hundred (1800) children will participate in the study. Each site will enroll up to 90 participant's total or 1-2 participants/month for a total study enrollment period of 57 months (some sites completed regulatory requirements well into the recruitment period)

**c. Inclusion Criteria**

1. Inpatient or outpatient age 8-19 years inclusive; participants must live with a parent, guardian, or caregiver;
2. Fluent in English;
3. Diagnosed or told by a clinician that they have any of the following bipolar spectrum disorders (BSD): bipolar I, bipolar II, unspecified bipolar and related disorders, Disruptive Mood Dysregulation Disorder (DMDD), cyclothymic disorder, other specified bipolar and related disorders, as well as mood disorder not otherwise specified (if diagnosed in the past as per DSM-IV);
4. Body mass index  $\geq 85\text{th}\text{ percentile}$  for age and sex by standard growth charts;
5. Received a new or ongoing prescription for at least one SGA (i.e., olanzapine, clozapine, risperidone, quetiapine, aripiprazole, ziprasidone, iloperidone, lurasidone, paliperidone, brexpiprazole or cariprazine) that is not prescribed as a PRN medication;

**Exclusion Criteria:**

1. Patients will be excluded if they have had exposure to a total daily dose of MET 1000 mg bid for at least 2 weeks in the past 3 months;
2. Patients will be excluded if they could not tolerate MET during the recommended titration schedule outlined in the protocol;
3. Major neurological or medical illnesses that affect weight gain (e.g., unstable thyroid disease) or require a systemic medication that might impact weight or glucose regulation (e.g., diabetes mellitus [insulin], chronic renal failure [steroids]);
4. If lab results are available in the last 6 months, then a fasting serum glucose  $\geq 126\text{ mg/dL}$  on 2 occasions prior to or during screening, indicating need for prompt treatment.
5. If lab results are available in the last 6 months, then a serum creatinine  $\geq 1.3\text{ mg/dL}$  on 2 occasions during screening and/or follow-up, indicating potential impairment of renal functioning
6. Pregnant or breast feeding;
7. Based on their clinician's assessment, children and caregivers who are unable to complete screening/baseline assessments for any reason;

If a patient does not have fasting glucose or renal lab results within 6 months prior to their baseline visit, then every attempt will be made to obtain labs prior to starting metformin. However, patients will not be excluded from the study if they are unable to get serum creatinine or glucose. Renal dysfunction is extremely rare in otherwise healthy children and adolescents, and in a clinical setting renal panels are not typically done prior to starting metformin, unless there is a reason to suspect kidney disease.

The initial rationale for requiring normal glucose prior to starting metformin was that patients who are hyperglycemic may need to receive metformin + LIFE rather than LIFE alone. However, if a patient does not have a normal glucose available prior to randomization, but meets all other study criteria, we will continue to collect data from the patient and administer the treatment to which they have been randomized, so that at a minimum they will receive LIFE. We will also strongly encourage their clinician to emphasize the importance of obtaining fasting glucose levels. If, however, lab results are available in the last 6 months, patient with a fasting glucose  $\geq 126$  mg/dL on 2 occasions will be excluded and referred to their primary care clinician for prompt evaluation for Type II diabetes. Including these patients, rather than waiting until they get their glucose level checked, will ensure that at least the patient will receive LIFE while we encourage the clinician to engage the patient to get fasting metabolic labs. At any point in the study of a patient has a fasting glucose  $\geq 126$  mg/dL on 2 occasions, they will be immediately referred to their primary care physicians and possibly endocrinology.

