1. Patients will be excluded if they have had exposure to a total daily dose of MET 1000 mg bid for at least 2 weeks in the past 3 months;
2. Patients will be excluded if they could not tolerate MET during the recommended titration schedule outlined in the protocol;
3. Major neurological or medical illnesses that affect weight gain (e.g., unstable thyroid disease) or require a systemic medication that might impact weight or glucose regulation (e.g., diabetes mellitus [insulin], chronic renal failure [steroids]);
4. If lab results are available in the last 6 months, then a fasting serum glucose  $\geq 126 \text{ mg/dL}$  on two occasions prior to or during screening, indicating need for prompt treatment.
5. If lab results are available in the last 6 months, then a serum creatinine  $\geq 1.3 \text{ mg/dL}$  on two occasions during screening and/or follow-up, indicating potential impairment of renal functioning
6. Pregnant or breast feeding;
7. Based on their clinician's assessment, children and caregivers who are unable to complete screening/baseline assessments for any reason;

The enrollment rate will be approximately 1-2 patients/month/site for a recruitment time of 57 months.

**Randomization:** We will randomize 1800 patients (1:1 ratio) to either MET + LIFE or LIFE alone. All patients will receive a lifestyle intervention (LIFE) of brief standardized education. Once a patient is determined to meet the above criteria and has provided appropriate informed consent/assent, site staff will assign the participant a patient ID number. The site staff will then log on to the study's REDCap site and enter the Patient ID, and the following stratification factors: site, overweight or obese, previous SGA exposure, and sex of patient (transgendered patients will be randomized according to sex assigned at birth). REDCap has a built in mechanism that prevents duplication of subject ID numbers.

Once all stratification factors have been entered, the REDCap randomization module will return the next assignment for the appropriate strata.

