#### **Laboratory Measures:**

Site staff will collect and report any lab results that are obtained as part of the patient's clinical care. Laboratory tests will be suggested according to clinical practice guidelines, but will not be required for patients enrolled in MOBILITY, with the exception of a pregnancy test for all girls who have reached menarche and who are randomized to metformin. Additionally, since patients receive their treatment at mental health treatment facilities throughout the country and MOBILITY is a pragmatic study, patients may have laboratory tests performed at any laboratory facility that they typically would as part of their routine clinical care. We will collect the results of the laboratory tests once they are available in medical records. Therefore, we will not require CLIA certificates or other regulatory documents for each laboratory facility. Table 2 (at intervals that reflect standard clinical care) indicates the recommended lab measures according to practice guidelines.

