Screening laboratory tests recommended include renal and hepatic function tests, electrolytes, CBC and thyroid stimulating hormone (TSH), as per Table 2. However, we will collect any results of labs performed within the last six months, if available. The only mandatory test for screening will be a pregnancy test in girls of menarche.

Every attempt will be made to encourage clinicians to obtain laboratory testing prior to starting metformin, however, patients who have not had baseline labs will continue to be followed in MOBILITY.

Kiddie-SADS-Present and Lifetime (K-SADS-PL 2013): After discussion with our patient/parent partners and site clinicians, we determined that the appropriate study population is all patients who receive a clinical diagnosis of a BSD, as these patients will typically receive SGA treatment regardless of whether they meet full DSM criteria. However, it was decided that using a structured research interview would provide an opportunity to examine concordance of clinical and research diagnoses and to assess HTE (i.e., do youth with a research diagnosis respond to MET differently than those with only a clinical diagnosis because risk for overweight/obesity and metabolic disorder may be higher for those with a research BSD diagnosis). Therefore, BSD diagnoses will be confirmed with the mood modules of the K-SADS-PL, a semi-structured diagnostic interview with established test-retest reliability. (Interviewers will be trained by qualified personnel. Trained staff at the respective coordinating centers who are not associated with the clinical sites will administer the interview separately to guardians and patients, if > 12 years old). Based on feedback from the clinical sites, we determined that having their staff administer the K-SADS-PL might create diagnostic confusion, therefore, we will develop a mechanism that clinicians will be provided with the K-SADS-PL diagnoses after participants have reached Month 6 of study participation.

Table 1. Metformin (MET) Titration		
	<50kg AM/PM	≥50kg AM/PM
Week 1	0/500mg	0/500mg
Week 2	0/500mg	0/500mg
Week 3	500/500mg	500/500mg
Week 4	500/500mg	500/500mg
Week 5	500/1000mg	500/1000mg
Week 6	500/1000mg	500/1000mg
Week 7	500/1000mg	1000/1000mg
Week 8	500/1000mg	1000/1000mg

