Caregiver Strain Questionnaire (P)	X	X	X	X	X	X	X	X	X	X	X
Other recommended measures											
Vital Signs [blood pressure, heart rate] (C)	X	X	X	X	X	X	X	X	X	X	X
Other recommended laboratory measures: d,e thyroid, renal and liver panels, pregnancy test, CBC, and Vitamin B12 (C)	X				X						X
Suicidality, Patient Health Questionnaire (PHQ)-Item 9 (C)	X	X	X	X	X	X	X	X	X	X	X
Zucker Hillside Side Effects Form (C)	X				X						X
Total Time/Visit for Youth Questionsf (minutes)	15-20	5	5	5	15-20	5	7	5	7	5	15-20
Total Time/Visit for Caregiver Questionsf (minutes)	15-20	5	5	5	15-20	5	7	5	7	5	15-20

P= Caregiver; Y= Youth, C= Clinician. Kiddie-SADS-Present and Lifetime-PL 2013;

aKSADS will be performed at any time point after enrollment.

bBaseline fasting serum glucose is highly recommended, however, results within the past six months will be acceptable.

cItems from the PROMIS=Patient Reported Outcome Measurement Information System;

dAny labs completed within the past 6 months are acceptable except for pregnancy test;

At baseline a negative serum or urine pregnancy test is required in girls who have reached menarche prior to prescribing metformin.

eLabs are recommended, however these are not required to start or continue in the study.

fClinician and other assessments (e.g. labs, vitals) are part of a routine clinical visit and therefore, do not add time.

Our population will be  $\geq$ 85%ile BMI (weight of such 8- and 9 year-olds will likely be comparable to an average 10-year-old child); 2) MET has a favorable side effect profile; and 3) prior reports as well as the investigators' previous experiences with the safe and well-tolerated use of MET in patients  $\geq$ 8 years old. All patients will have a renal panel prior to starting MET to evaluate for renal impairment that would preclude use of MET.

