The basic model for outcomes will be a GLMM with change from baseline to either 6- or 24- months as the dependent variable. Independent variables will include fixed-effect terms for randomized treatment group (MET), baseline value of the outcome, and random site effects. For HTE analyses, a baseline value-by-MET interaction (to assess HTE due to baseline status) will be included, and for particular domains additional continuous or categorical covariates and treatment-by-covariate interaction terms will be added to assess HTE. Outcomes within each domain will share the same set of HTE terms, specified in the Specific Aims. Because the subgroups are in general correlated (e.g., duration of SGA treatment, weight gain history and psychotropic weight burden will be correlated with baseline BMI), we will include multiple first-order HTE terms simultaneously (to assess heterogeneity independently attributable to each moderator), but will also fit separate models for each term to gauge the impact of this correlation on our conclusions. Higher-order treatment-by-covariate interactions will not be included a priori, but will be explored with rigorous adjustment for multiple testing, using step-down testing (removing highest-order interaction terms first) or information criteria based on penalized likelihoods to guide model selection.

**Marginal Structural Modeling for Causal Inference:** SA1 concerns the overall and sub-group specific effects of MET on abrogation of weight gain (with changes in BMI z-score from baseline as outcomes) and metabolic health, particularly metabolic syndrome and its component criteria. BMI and adherence measures are obtained at all study visits, so our models for these measures will use all available observations by treating the longitudinal series of changes in these variables and SGA treatment as dynamically dependent on each other. We will use marginal structural models to address this bi-directional dependence, computing the probability of SGA treatment regimen change at each visit within weight gain treatment regimen groups and using appropriately normalized versions of the inverse of the probability as the stabilized weights.

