course of the study. Our study endocrinologists (Drs. [name] and [name]) will also be available throughout the study should any site clinicians have questions regarding MET use. We will also educate site clinicians that it is part of standard of care to obtain labs prior to initiating MET. In particular, since MET is excreted by the kidneys, if a patient has creatinine  $\geq 1.3$  mg/dL on 2 occasions, they will be excluded from study participation and referred to their primary care clinician. Since lactic acidosis is a very rare side effect of MET and primarily occurs in elderly diabetic patients with significant renal insufficiency or congestive heart failure, we will inform clinicians of the risk and associated symptoms, but explain that we are excluding those most at risk and to our knowledge, that there have been no reports of lactic acidosis in youth. Additionally, we will encourage site clinicians to inform patients that excessive use of alcohol needs to be avoided as alcohol potentiates the effects of metformin on lactate metabolism (patients may be users of alcohol) and metformin should be discontinued prior to any IV radiocontrast study or surgical procedure. Additionally, to guard against risk, if a patient has two 8-hour fasting glucose levels  $\geq 126$  mg/dL, they will be referred to their primary care clinician (and if at screening they will not be included in the study), so that they may be evaluated for type II diabetes.

**Blood Draws:** We will recommend that only trained and certified phlebotomists draw blood at a certified laboratory facility.

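### For lab-based secondary outcomes, the analysed patients can differ by arm: the firmest push for labs is timed to starting metformin, and the models need a baseline lab

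*Combined protocol and SAP*

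**What the plan says.** **Labs are optional.** Laboratory Measures states: "Laboratory tests will be suggested according to clinical practice guidelines, but will not be required for patients enrolled in MOBILITY". Table 2 recommends insulin, lipids, glucose and HbA1c at baseline and at months 6, 12, 18 and 24 in both arms. It requires none of them and accepts results from the past six months.

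**Several places time the effort to metformin.**
- Exclusion Criteria, for patients without a glucose or renal result in the six months before baseline: "then every attempt will be made to obtain labs prior to starting metformin". A patient whose labs cannot be obtained is still included.
- Screening/Baseline Procedures: "Every attempt will be made to encourage clinicians to obtain laboratory testing prior to starting metformin".
- Protection Against Risks: "We will also educate site clinicians that it is part of standard of care to obtain labs prior to initiating MET".
- The text below Table 2: "All patients will have a renal panel prior to starting MET to evaluate for renal impairment".

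**One paragraph is neutral between arms.** The end of the Exclusion Criteria section lets a patient without a normal glucose be randomised and treated as assigned. It also asks that clinicians be encouraged to obtain fasting glucose and fasting metabolic labs. It names no arm and no time point.

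**Analysis.** Analyses of Specific Aims models change from baseline to 6 or 24 months. The terms are randomised group, "baseline value of the outcome, and random site effects". Multiple imputation is described only for electronic adherence. The supplied text gives no rule for a missing baseline lab.

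**The concern.** Randomisation makes the arms comparable as randomised. It does not protect a subset chosen afterwards by a process that can work differently in each arm. Here membership of the subset is having a baseline lab, and part of the effort that decides it is tied to a drug that only one arm is assigned at baseline.

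What is at stake is the metabolic half of H1.1, that MET leads to fewer adverse metabolic outcomes at 6 and 24 months. Three of the five metabolic syndrome criteria (triglycerides, HDL, glucose) are labs. If testing were routine in MET but selective in LIFE, a difference in these outcomes could not be cleanly separated from a difference in who was tested.

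**Working it through.** The plan gives no expected lab capture, effect size or SD for the metabolic outcomes, so there is no stated figure to reproduce.

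**1. Timing.** The metformin-linked passages set the deadline at the first dose, not at randomisation. Since labs may be absent at randomisation, the effort can follow allocation. The LIFE arm is not assigned metformin. Its clinicians may start it at their discretion after a recommended initial 3 months, which is too late to supply a baseline value.

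**2. Entry to the model.** With change from baseline as outcome and baseline as covariate, a missing baseline lab removes the patient from the model for that lab.

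**3. Scope.** Affected: fasting glucose, lipids, insulin (and HOMA-IR derived from it), HbA1c, and metabolic syndrome through its lab criteria. Not affected: the overall BMI z-score comparison and blood pressure, which are not labs.

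**4. Illustration with no true effect.** From the plan: "We will randomize 1800 patients (1:1 ratio) to either MET + LIFE or LIFE alone", so 1800/2 = 900 per arm. Everything else is assumed.

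- Analysable n = 900 × capture rate.
- Minimum detectable difference (MDD) = (1.960 + 0.842) × √(1/n_MET + 1/n_LIFE), for two-sided 5% and 80% power. For 70%/50% this is 2.802 × √(1/630 + 1/450) = 0.173 SD.
- Simulation of 2,000,000 patients: latent risk U is standard normal; baseline lab B = 0.5U + √0.75·e₁; change D = gU − 0.3B + e₂, with g = 0.3 (0.5 in the last row). The log-odds of having a baseline lab rise with U at an arm-specific slope. D is regressed on arm and B among tested patients only. Negative values favour MET, because higher risk was assumed to mean a worse change.

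| Capture MET/LIFE | Analysable n | MDD (SD) | Slope on U, MET/LIFE | False effect (SD) |
|---|---|---|---|---|
| 50%/50% | 450/450 | 0.187 | 0.7/0.7 | 0.00 |
| 70%/50% | 630/450 | 0.173 | 0/0 | 0.00 |
| 60%/50% | 540/450 | 0.179 | 0.5/0.7 | −0.03 |
| 70%/50% | 630/450 | 0.173 | 0.3/0.7 | −0.05 |
| 80%/50% | 720/450 | 0.168 | 0/0.7 | −0.07 |
| 80%/30% | 720/270 | 0.200 | 0/0.7 | −0.10 |
| 80%/30% | 720/270 | 0.200 | 0/1.0 (g = 0.5) | −0.21 |

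Hand check of the fourth row: mean U among the tested is 0.085 in MET and 0.314 in LIFE, a difference of −0.229. The share of U not explained by B is 1 − 0.5² = 0.75. The SD of D is √(0.09 + 0.09 − 0.09 + 1) = 1.044. So 0.3 × 0.75 × (−0.229)/1.044 = −0.049, close to the simulated −0.051.

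The second row shows that unequal capture alone gives no bias. The first shows that selection that is the same in both arms gives none either.

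**5. What drives testing matters.** In a further null simulation, also on assumed settings, the planned model gave about 0 when testing followed the baseline lab value itself, about −0.03 SD when it followed BMI, and about −0.15 SD only when it followed the later outcome. A model that treats baseline as a response, and so keeps untested patients, gave a spurious 0.05 to 0.07 SD when testing followed the unobserved baseline lab. Neither model is safe under every mechanism.

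**The case against.** **LIFE patients are prompted too.** A reader might infer that only MET patients are asked for labs. The documents do not support that. The end of the Exclusion Criteria encourages fasting metabolic labs whatever the arm, Table 2 recommends the same labs for all and calls baseline fasting glucose highly recommended, and the Blood Draws text encourages draws generally. This softens the asymmetry. It does not remove it, since none of it gives LIFE a pre-treatment deadline.

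**The metformin-linked wording is mostly about safety labs.** The Exclusion Criteria trigger names glucose and renal results, the training text gives renal excretion as its reason, and the screening sentence follows a list of renal, hepatic, electrolyte, blood count and thyroid tests. Only fasting glucose clearly overlaps an outcome. That lipids, insulin and HbA1c would be drawn at the same time is plausible but is an inference. This stands, and it lowers confidence in the size of any effect.

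**A spurious gap of several points in metabolic syndrome is tempting to claim.** Suppose 30% prevalence, with affected patients 1.1 times as likely to be tested in MET and 1.5 times in LIFE. Prevalence among the tested is then 0.33/(0.33 + 0.70) = 32.0% against 0.45/(0.45 + 0.70) = 39.1%. But that is a baseline imbalance, and the planned model adjusts for baseline. If testing depends on baseline status alone, follow-up risk within each baseline status is equal across arms and the adjusted difference is zero. With these inputs, about 5 points remain only if testing follows follow-up status, and the schedule recommends month 6 and 24 labs alike in both arms.

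**Selective testing in LIFE is not documented.** Nothing states that LIFE clinicians would test mainly patients who look metabolically worse.

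**Pragmatism.** More prompting pulls against minimal interference with practice. A single request before randomisation, with labs still optional, is a small departure.

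**Conclusion.** The weakness holds for lab-based secondary outcomes only. Entry to their models requires an optional baseline lab, and the strongest effort to obtain labs can fall after randomisation and acts mainly in the MET arm. The analysed patients can therefore differ by arm; the documents do not show that they will.

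Bias needs two further conditions: the reasons for testing differ by arm, and they relate to metabolic course beyond the adjusted baseline value. If either fails, the planned model is unbiased on this account. The size is unknown because no capture rates are given. The −0.03 to −0.10 SD in most of the selective scenarios, and −0.21 SD in the most extreme, rest wholly on assumed capture and selection. For scale, the detectable differences in those scenarios are 0.17 to 0.20 SD.

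Separately, the statement below Table 2 that all patients have a renal panel before MET conflicts with Screening/Baseline Procedures and the Exclusion Criteria, under which labs are not a condition. Those passages must be reconciled.

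**What to change.** **Screening/Baseline Procedures and Exclusion Criteria.** Make the request for optional baseline outcome labs (fasting glucose, lipids, insulin, HbA1c) the same for both arms and place it before randomisation. Count as baseline only results obtained before randomisation. This needs no change to the pre-metformin safety wording; the sponsor should reconcile the renal-panel statements separately.

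**Analyses of Specific Aims.**
- Add baseline BMI z-score and blood pressure to the lab-outcome models, so that testing driven by these visible measures is accounted for.
- Beside the planned model, add an analysis that keeps patients without a baseline lab: a longitudinal model with baseline as a response and equal baseline means by arm for continuous labs, and multiple imputation of the components for metabolic syndrome, both using BMI z-score and blood pressure as auxiliaries.
- Do not replace the planned model. The two rely on different missingness assumptions, and agreement between them is the useful evidence.

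**Reporting.** Give lab capture by arm at baseline, month 6 and month 24.

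**Cost.** Slightly more prompting before randomisation and some extra analysis. Labs stay optional. The analysis and reporting parts need no patient contact, so they remain possible even after recruitment has ended.
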